2.3. Treatment Descriptions

2.3.1. Plamotamab (XmAb13676) Product Description

Plamotamab (XmAb13676) is a humanized bispecific antibody (bsAb) that binds both CD3 and the tumor antigen CD20 in order to recruit cytotoxic T cells to kill CD20 tumor cells. Plamotamab has been designed to maintain full-length humanized monospecific antibody properties in a bsAb, enabling the design of stable molecules with favorable in vivo half-life, and allowing for the use of standard antibody production methods.

Antibody discovery programs at Xencor have demonstrated that several bsAbs based on this format are highly but selectively active towards target cells in primate models. See [Section 2.4](#) for human experience with plamotamab.

2.3.2. Tafasitamab Product Description

Tafasitamab (tafasitamab-cxix) is a CD19-directed cytolytic antibody indicated for use in the US in combination with lenalidomide for the treatment of adult patients with R/R DLBCL not otherwise specified (NOS), including DLBCL arising from low-grade lymphoma, and who are not eligible for ASCT. Tafasitamab is also approved in the EU and is indicated in combination with lenalidomide followed by tafasitamab monotherapy for the treatment of adult patients with relapsed or refractory DLBCL who are not eligible for ASCT. Tafasitamab is a humanized CD19-directed cytolytic monoclonal antibody that contains an IgG1/2 hybrid Fc-domain with 2 amino acid substitutions to modify the Fc-mediated functions of the antibody. It is produced by recombinant DNA technology in mammalian cells (Chinese hamster ovary). Tafasitamab has a molecular weight of approximately 150 kDa (see US [Monjuvi[®] PI, 2021](#); EU [Minjuvi[®] SmPC, 2021](#)).

2.3.3. Lenalidomide Product Description

Lenalidomide, a thalidomide analogue, is an immunomodulatory agent (IMiD[®]) with antiangiogenic and antineoplastic properties. It is indicated for the treatment of adult patients with multiple myeloma, myelodysplastic syndromes, mantle cell lymphoma, follicular lymphoma, and marginal zone lymphoma. See [Revlimid[®] PI, 2021](#) or [Revlimid[®] SmPC, 2022](#) for more information.

2.4. Human Experience with Plamotamab

Plamotamab is being studied in a Phase 1 study, XmAb13676-01 (A Phase 1 Multidose Study to Evaluate the Safety and Tolerability of XmAb[®]13676 in Patients with CD20-Expressing Hematologic Malignancies). As of 18 August 2021, a total of 96 subjects have been treated with plamotamab in the XmAb13676 01 study at weight-based dose levels of 0.7 to 360 µg/kg and flat dose levels of 0.8 to 50 mg. Of those 96 subjects, 80 were in the NHL group and 16 were in the CLL group. Adverse events (AEs) have been reported in 100% of the 80 NHL subjects. The most frequent AEs (>20%) in the NHL group were cytokine release syndrome (51/80, 63.8%), pyrexia (43/80, 53.8%), anemia (34/80, 42.5%), fatigue (24/80, 30.0%), nausea (21/80, 26.3%), diarrhea and cough (20/80, 25.0%), constipation (19/80, 23.8%), chills, headache, hypokalemia, and thrombocytopenia, (18/80, 22.5%), asthenia, dizziness, dyspnoea, hypotension, and neutropenia (17/80, 21.3%). Cytokine release syndrome (CRS), a predicted toxicity for this class of drugs, has occurred in subjects treated at 7.5, 10, 20, 25, 45, 50, 80, 125, 170, 250 µg/kg and at 0.8, 2, 20, 35 mg; however, CRS has not yet been seen at the highest dose levels of 360 µg/kg and 50 mg, in this study. The pattern of these events has differed in the NHL versus the CLL cohorts in this study.

2.4.1. Non-Hodgkin's Lymphoma: Escalation Cohorts

In the NHL escalation cohorts, the events have been predominantly Grade 1 or 2 in severity, with the exception of 4 out of 80 (5.0%) subjects who each experienced ≥ Grade 3 CRS, assessed according to American Society for Transplantation and Cellular Therapy (ASTCT) 2019 criteria, all associated with the first infusion of plamotamab. Manifestations of CRS have included fever, hypotension, tachycardia, chills, rigors, hypertension, headache, hypoxia, and elevations of liver enzymes. During the XmAb13676-01 study, cases of transaminase elevation, with or without bilirubin elevation, have occurred in the setting of CRS. The events were transient and reversible, with the transaminase and bilirubin levels returning to normal usually within 5 days. Five subjects (5/80, 6.3%) in the NHL cohort died during the study due to AEs, 3 due to COVID-19 (3/80, 3.8%), one of respiratory failure (1/80, 1.3%), and one due to unknown reasons (1/80, 1.3%).

2.4.2. Non-Hodgkin's Lymphoma: Flat-Dosing Cohorts

In the flat-dosing cohort (Cohort 1N-C, weekly titration of 0.8, 2, 20, 35 and 50 mg, followed by weekly dosing of 50 mg until Cycle 3 then every-two-week dosing of 50 mg) of NHL subjects, data are available for 14 subjects as of 18 August 2021. Of those subjects, the most frequent AEs (> 20%) were cytokine release syndrome (8/14, 57.1%), nausea (7/14, 50.0%), pyrexia and anemia (6/14, 42.9%), asthenia (4/14, 28.6%), fatigue, diarrhea, headache, dizziness, dyspnoea, hypotension, decreased appetite, alanine aminotransferase (ALT), increased back pain, peripheral

oedema, and aspartate aminotransferase (AST) increased (3/14, 21.4%). All CRS events, assessed according to ASTCT 2019 criteria, were Grade 1 or 2. In this cohort, manifestations of CRS occurring in more than 1 subject included pyrexia (7/8, 87.5%), hypotension (5/8, 62.5%), hypoxia and tachycardia (3/8, 37.5%), and headache (2/8, 25.0%). Anemia and lymphopenia were the only Grade 3 or 4 events reported in more than 1 subject (2/14, 14.3%). A single subject (1/14, 7.1%) died of COVID infection in this cohort.

Efficacy in the NHL population as measured by overall response rate (objective response rate [ORR], complete response [CR] plus partial response [PR]) and was observed in nearly all cohorts, with responses seen more consistently in cohorts with a top dose of greater than 80 µg/kg. [Table 2](#) below presents the responses by cohort, as of 18 August 2021, for cohorts with a top dose of greater than or equal to 80 µg/kg in the efficacy evaluable population for NHL. The proposed plamotamab flat dosing regimen for the XmAb13676-03 study is represented below as “50 mg.”

Table 2: Overall Response Rate, Complete Response and Disease Control Rate for Overall Population and by Top Dose Level in Subjects with NHL from Study XmAb13676-01

Top Dose/Response	Efficacy Evaluable Population
Overall	
ORR	24/55 (43.6)
CR	11/55 (20.0)
DCR	32/55 (58.2)
80 µg/kg	
ORR	1/5 (20.0)
CR	0/5
DCR	2/5 (40.0)
125 µg/kg	
ORR	6/16 (37.5)
CR	5/16 (31.3)
DCR	10/16 (62.5)
170 µg/kg	
ORR	4/8 (50.0)
CR	2/8 (25.0)
DCR	5/8 (62.5)
250 µg/kg ^a	
ORR	6/12 (50.0)
CR	1/12(8.3)
DCR	5/12 (41.7)
360 µg/kg	
ORR	2/5 (40.0)
CR	1/5 (20.0)
DCR	4/5 (80.0)
50 mg	
ORR	5/9 (55.6)
CR	2/9 (22.2)
DCR	5/9 (55.6)

CR = complete response; DCR = disease control rate; ORR = objective response rate.

^a One subject received a single priming dose of 25 µg/kg and achieved a PR.

Note: Efficacy population is defined as Subjects who did not withdraw prior to 2 cycles and completed at least 75% doses (6 out of 8 doses) and have post-baseline response assessment data available; or subjects who withdrew due to AEs/death; or subjects who withdrew other than AEs/death and have completed at least 75% doses of the first cycle (3 doses out of 4).

DCR includes Complete Metabolic Response, Complete Response, Partial Metabolic Response, Partial Response, No Metabolic Response, and Stable Disease.

2.4.3. Recommended Phase 2 Dose

The Phase 1 study, XmAb13676-01 demonstrated that plamotamab is well tolerated up to the highest dose level tested and has activity in R/R DLBCL. Notably, the flat dosing Cohort 1N-C (weekly titration of 0.8, 2, 20, 35, and 50 mg, followed by weekly dosing of 50 mg until Cycle 3 then every-two-week dosing of 50 mg) had an acceptable rate of CRS, with no Grade 3 or 4 CRS and no CRS events after start of every 2-week dosing. Among the subjects in the 1N-C cohort, Grade 3 and 4 toxicities were limited to anemia, liver enzyme increases, and cytopenias, all at rates of less than 20%. No dose-limiting toxicities were observed among the 14 treated subjects.

[figure not shown]
Preliminary exposure-response analysis based on the plamotamab pharmacokinetics (PK) and corresponding responses (ORR, CRS, others) in study XmAb13676-01 indicate a target trough concentration (C_{trough}) threshold of approximately 350 ng/mL (95% CI) to minimize the risk of CRS and a target C_{trough} threshold of approximately 650 ng/mL (95% CI) to maximize the probability of objective response. A population PK model was developed for plamotamab using interim data (April 2020) from the Phase 1 Study XmAb13676-01 that included plamotamab concentrations, actual sampling times, dosing histories, and baseline body weights from 53 subjects with NHL. Based on this model, the proposed dosing schemes in Part A of this study (XmAb13676-03) were simulated (predictions for high dose group shown in [Figure 1](#)). Population PK based predictions indicate that at the 20 mg dose, 77% of subjects exceed the safety threshold of 350 ng/mL, but only 52% of the subjects exceed the efficacy threshold of 650 ng/mL. At the 50 mg dose, 93% of subjects exceed the safety threshold of 350 ng/mL and 83% of the subjects exceed the efficacy threshold of 650 ng/mL. Based on these results, 50 mg dose group is more likely to provide a robust response across the population, but there exists significant variability in the estimate for target thresholds, and therefore further characterization of exposure response is desired at a range of concentrations in this study. Accordingly, this study evaluates two dose levels of plamotamab 20 mg and 50 mg at steady state that have been demonstrated to be well tolerated and active in the Phase 1 study.

This study includes a safety run-in that evaluates 2 dose levels of plamotamab with the standard doses of tafasitamab and lenalidomide. In addition to the recommended Phase 2 dose (RP2D), the study begins with a regimen that titrates to 20 mg: weekly titration of 0.8, 2, and 20 mg, followed by weekly dosing of 20 mg until Cycle 3 then every-2-week dosing of 20 mg. The titration from low minimally active dose to pharmacologically active doses was chosen to mitigate the risk of CRS based on clinical experience with plamotamab and other CD3-directed antibodies ([Hosseini, 2020](#); [Hutchings, 2021](#)).

Tafasitamab is an Fc-modified monoclonal antibody that binds to CD19 antigen expressed on the surface of pre-B and mature B lymphocytes and on several B-cell malignancies, including DLBCL. Upon binding to CD19, tafasitamab-cxix mediates B-cell lysis through apoptosis and immune effector mechanisms, including antibody-dependent cellular cytotoxicity and antibody-dependent cellular phagocytosis. In a Phase 1 clinical trial ([Woyach, 2014](#)), tafasitamab given at 12 mg/kg every 4 days reduced peripheral blood B cell counts by 97% after 8 days of treatment in patients

with relapsed or refractory DLBCL. Given that tafasitamab may promote B cell depletion, which could mitigate CRS with the addition of plamotamab + lenalidomide to the regimen, an 8-day, 2-dose run-in of tafasitamab at 12 mg/kg is included before C1D1. Other than the 2-dose tafasitamab monotherapy run-in, tafasitamab and lenalidomide will be administered according to the package inserts (PIs) or Summary of Product Characteristics (SmPCs; [Monjuvi[®] PI, 2021](#); [Minjuvi[®] SmPC, 2021](#); and [Revlimid[®] PI, 2021](#); [Revlimid[®] SmPC, 2022](#)).

Figure 1: Log Scale Simulated Median Concentrations and 90% Prediction Intervals for Flat Dose and Schedule.

For doses beyond Week 12, the blue area above the line at 0.6 $\mu\text{g}/\text{mL}$ illustrates the prediction that 85% of subjects maintain Q2W steady state troughs above the 0.6 $\mu\text{g}/\text{mL}$ trough chosen to preserve benefit.

2.4.4. Benefit/Risk Assessment

It is anticipated that the addition of plamotamab to the combination of tafasitamab and lenalidomide will enhance efficacy, through higher response rates and longer time to progression due to the engagement of both CD19 and CD20 antigens with nonoverlapping mechanisms of resistance.

Plamotamab monotherapy demonstrated responses across nearly all dose levels above 80 $\mu\text{g}/\text{kg}$ maximum dose, see [Table 2](#). Within the NHL Efficacy Population, responses were observed in 24/55 (43.6%) with 11/55 subjects (20%) subjects achieving a CR. Further, responses were observed in 5/9 (55.6%) subjects in the NHL Efficacy Population treated at the RP2D. Tafasitamab and lenalidomide established efficacy in R/R DLBCL in a recent Phase 2 study with a response rate of 57.5% with 40% achieving a CR. PFS was 11.6 months ([Duell, 2021](#)). Regulatory approvals have been granted in the US and EU.

Although the RP2D of plamotamab monotherapy has been identified, the appropriate dose in combination with tafasitamab and lenalidomide has not been established. To assess the safety of plamotamab when it is used in combination with tafasitamab and lenalidomide, a safety run-in phase is planned in this study. The safety run-in phase will enroll subjects starting at a lower dose of plamotamab (see [Table 3](#)) prior to enrolling subjects at the RP2D. Safety will be assessed before proceeding to the randomized part of the study.

Other safety measures have been implemented. The step-up dosing regimen used in this study reduced CRS events to Grade ≤ 2 in the Phase 1 trial. In addition, the study requires the separation of the dosing of tafasitamab, plamotamab, and lenalidomide as well as including dose modifications of each product for specific toxicities, along with management guidelines for those toxicities.

These safety measures along with the efficacy observed with both plamotamab and tafasitamab in combination with lenalidomide, present a favorable benefit-risk ratio for subjects enrolling in this study.

3. TRIAL OBJECTIVES AND PURPOSE

3.1. Primary Objectives

To determine the safety and efficacy of the combination of plamotamab, tafasitamab, and lenalidomide compared to tafasitamab and lenalidomide in adult subjects with R/R DLBCL.

3.2. Secondary Objectives

The secondary objectives of the study are to compare a combination of plamotamab, tafasitamab, and lenalidomide to tafasitamab and lenalidomide as follows:

1. To compare rates of objective response (ORR = CRR + partial response rate [PRR]) by Blinded Independent Review Committee (BIRC) and Investigator per Lugano 2014 criteria
2. To compare overall survival (OS)
3. To compare time to treatment failure (TTF)
4. To assess duration of response (DOR) among subjects achieving an objective response (CR + PR) and among subjects achieving a CR by BIRC
5. To compare the PFS, as determined by the Investigator
6. To assess the incidence, timing, and severity of CRS by following CRS-related AEs including incidence and grade of AEs and incidence of serious adverse events (SAEs)
7. To assess the incidence, timing, and severity of neurological AEs and incidence and grade of immune effector cell-associated neurotoxicity syndrome

8. To assess the dose intensity of tafasitamab and lenalidomide in Part 1 when given in combination with plamotamab
9. To assess the safety profile of a combination of plamotamab, tafasitamab, and lenalidomide in Part 2 as determined by the incidence and severity of treatment-emergent adverse events (TEAEs), in adult subjects with R/R DLBCL

3.3. Exploratory Objectives

The exploratory objectives of the study are as follows:

1. To assess the PK of plamotamab and tafasitamab
2. To assess the potential immunogenicity of plamotamab and tafasitamab
3. To explore the association of baseline CD19 and CD20 levels, molecularly defined DLBCL subtypes, minimal residual disease (MRD) as measured by circulating tumor DNA (ctDNA), and immune cell frequency, activation status, and function with clinical outcomes
4. To evaluate biomarkers of CRS (including but not limited to serum cytokine levels) with clinical outcomes
5. To assess potential associations between clinical outcomes and biologically and clinically defined subgroups, including but not limited to randomization strata and time since last rituximab treatment

3.4. Purpose of Study

The combination of tafasitamab in combination with lenalidomide has been granted accelerated approval in the US for use in patients with R/R DLBCL, NOS. Tafasitamab is an Fc-modified monoclonal antibody that binds to CD19 antigen expressed on the surface of pre-B and mature B lymphocytes and on several B-cell malignancies, including DLBCL. In combination with lenalidomide in a single-arm clinical trial (NCT02399085), tafasitamab had a 57.5% response rate in R/R DLBCL with a median DOR of 43.9 months and median PFS of 11.6 months (Duell, 2021). Plamotamab is a humanized bsAb that binds both CD3 and the tumor antigen CD20 in order to recruit cytotoxic T cells to kill CD20 tumor cells. In an ongoing Phase 1 study (Study XmAb13676-01, NCT02924402), plamotamab has produced durable responses in subjects with R/R DLBCL.

It is hypothesized that the engagement of both CD19 and CD20 antigens will enhance efficacy outcomes in this population, due to nonoverlapping mechanisms of resistance. Further, this combination activates and expands the innate immune system and adaptive effector cells as well as modulates the tumor microenvironment. These characteristics support and warrant a study of the combination of plamotamab, tafasitamab, and lenalidomide. The trial first determines if the combination of the 3 products can be safely administered and to determine the dose for Part 2. The second part of this trial is designed to determine the improvement in efficacy, as measured by PFS,

of the standard of care for DLBCL, tafasitamab and lenalidomide, with the addition of plamotamab to tafasitamab and lenalidomide.

4. INVESTIGATIONAL PLAN

4.1. Overall Study Design

This is a randomized, multicenter, open-label, Phase 2 study of plamotamab combined with tafasitamab plus lenalidomide versus tafasitamab plus lenalidomide in adult subjects with DLBCL who have relapsed after or are refractory to at least 1 prior line of therapy, which must have included multi-agent chemoimmunotherapy inclusive of an anti-CD20 monoclonal antibody, and who are not candidates for ASCT, refuse ASCT, or relapse after ASCT.

A central pathologist reading will confirm the diagnosis of DLBCL retrospectively after enrollment, using archival or recently obtained tissue. Central radiology and clinical reviewers will assess objective disease response according to the Lugano 2014 ([Cheson, 2014](#)) guidelines. Details of the central review will be provided in an imaging charter outlining functions and processes. In addition, Investigator-assessed response will be captured in the clinical database, and concordance analyses will be performed. All subjects will be treated until progression or withdrawal for other reasons and then followed for OS up to 5 years.

This study will consist of 2 parts which will be performed sequentially, with Part 1 enrolling and evaluating subjects for safety and determination of dose and schedule before the start of Part 2.

4.1.1. Part 1: Single-Arm, Safety Run-In

Part 1 consists of a single-arm evaluation of the safety of the triple combination of plamotamab combined with tafasitamab plus lenalidomide in at least 40 subjects in 2 cohorts of a minimum of 20 subjects per cohort:

- Cohort 1A treats subjects with the triple combination at plamotamab dose level –1 ([Table 3](#)).
- Cohort 1B commences enrollment after the Cohort 1A completes enrollment. Cohort 1B treats subjects with the triple combination at plamotamab dose level 1 ([Table 3](#)).
- An initial safety evaluation is conducted after all subjects in Cohorts 1A and 1B either receive treatment, at a minimum, through C4D28 or are discontinued prior to C4D28 due to an AE or progressive disease.

After the initial safety evaluation of both Cohorts 1A and 1B, the pharmacologically optimal dose of plamotamab (dose level -1 or dose level 1) with an acceptable safety profile will be advanced to the randomized (Part 2) portion of the study.

Table 3: Cohort 1A and Cohort 1B Plamotamab Dosing Regimen

Cohort	Dose Level	Cycle 1 Day 1 (Priming Dose)	Cycle 1 Day 8	Cycle 1 Day 15	Cycle 1 Day 22	Cycle 2 Day 1	Cycle 2 Days 1, 8, 15, and 22	Cycle 3 and Subsequent Q2W Dosing
1A	-1	0.8 mg	2 mg	20 mg	20 mg	20 mg	20 mg	20 mg
1B	1	0.8 mg	2 mg	20 mg	35 mg	50 mg	50 mg	50 mg

Q2W = every 2 weeks.

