4.5.1. Part 1: Single-Arm Safety Run-In

During the Part 1 safety run-in, 40 subjects will be enrolled and treated with plamotamab and tafasitamab plus lenalidomide (ie, single-arm, uncontrolled). The subjects will be considered enrolled if they have signed the informed consent, are determined to be eligible, and receive the Day -8 tafasitamab priming dose.

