- Note that older subjects or those with significant comorbidities may be at higher risk of decompensation in this situation. When reactions occur in these vulnerable subjects, or in the case of rapidly progressing reactions, consider treatment with tocilizumab 8 mg/kg IV over 1 hour, with or without additional dexamethasone 10 to 20 mg IV (or equivalent).

Grade 3 and 4

- Stop the infusion and disconnect the infusion tubing from the subject.
- Administer additional dexamethasone 10 mg intravenously.
- Immediately give aggressive supportive care. Use pressors, fluids, oxygen, epinephrine or bronchodilators, ventilatory support, antipyretics, and analgesics as indicated.
- Treatment with tocilizumab, 8 mg/kg IV over 1 hour ([Hallek, 2018](#)), is encouraged for CRS due to the high risk of progression and permanent organ dysfunction.
- Hospital admission for observations is almost always indicated, usually to an intensive care unit, since an initial appearance of improvement may quickly yield to rapid decompensation.
- Subjects with Grade 3 CRS or infusion reaction may be rechallenged once resolved as described in [Section 4.7](#) and [Table 8](#). Subjects with recurrent Grade 3 or any Grade 4 reaction should not receive further plamotamab treatment but will continue to be followed on the protocol (ie, followed for long-term survival).
- Obtain an unscheduled blood sample for cytokine analysis during the event and approximately 4 hours later, unless scheduled cytokine monitoring is already in progress on the same visit day.
- Obtain an unscheduled sample for anti-drug antibodies (ADA) testing as close to the onset of the event as possible, at the resolution of the event, and approximately 28 days

following the event, unless scheduled cytokine monitoring is already in progress on the same visit day.

- Notify the Xencor Medical Monitor immediately.

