4.8. Criteria for Study Modifications

Part 1 consists of a 40-subject, two-cohort, single-arm evaluation of the safety of the triple combination. The Sponsor may adjust the dose and/or schedule for Cohort 2 based on the initial safety evaluation of Cohort 1A and 1B. The Sponsor will assess the data from both cohorts to determine the dose and/or schedule before beginning the randomized portion of the study.

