4.9. Independent Committees

4.9.1. Independent Data Monitoring Committee

The IDMC will periodically monitor the randomized portion of the study for safety considerations. The IDMC will consist of independent reviewers who are not directly involved in the conduct of the study and will advise the Sponsor of any trends or safety issues which may impact the study and/or the study subjects. The IDMC will operate according to a charter, which the committee will review and ratify before enrollment commences. The IDMC, at a minimum, will as follows:

- Consist of at least 2 oncologists + 1 statistician, all of whom are independent from the study personnel
 - Evaluate accumulating safety data during Part 2 for all enrolled and treated subjects after 50, 100, and 150 subjects have been randomized.

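### Nothing in the plan requires a review of Cohort 1A safety data before Cohort 1B subjects go above 20 mg of plamotamab

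*Protocol*

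**What the plan says.** Protocol 4.1.1 sets the sequence of the run-in: "Cohort 1B commences enrollment after the Cohort 1A completes enrollment". The synopsis and SAP 3.1.1 give the same trigger, and none of them attaches a safety condition. Under Protocol 4.5.1, a Part 1 subject is enrolled once consented and eligible and on having "receive the Day -8 tafasitamab priming dose", which is before any plamotamab.

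The planned looks across subjects all come later or cover something else:

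- The initial safety evaluation in 4.1.1 waits until every subject in both cohorts has been treated through C4D28 or has stopped earlier for an adverse event or progression. It decides which dose goes into Part 2.
- Section 4.8 says: "The Sponsor may adjust the dose and/or schedule for Cohort 2 based on the initial safety evaluation of Cohort 1A and 1B". No Cohort 2 is defined. The section then has the sponsor assess both cohorts together before randomization starts.
- Section 4.9.1 limits the monitoring committee: "The IDMC will periodically monitor the randomized portion of the study for safety considerations".

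On what is known about the dose, section 2.4.4 says: "Although the RP2D of plamotamab monotherapy has been identified, the appropriate dose in combination with tafasitamab and lenalidomide has not been established". Section 4.6 adds that the three drugs had not been given together in humans. Section 4.6.3 warns that falls in neutrophils and platelets could be deeper or longer with the combination.

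**The concern.** A lower-dose cohort that enrolls first protects later subjects only if someone looks at its data before the dose goes up. As written, 1B can open on the day the last 1A subject receives tafasitamab on Day -8. At least 20 subjects can then pass 20 mg without anyone having been required to look across 1A and decide that this is reasonable.

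What is at stake is combination toxicity from C1D22 onward, mainly cytopenias. These are the overlap that the protocol itself identifies. Table 7 gives all-grade neutropenia of 51% with tafasitamab/lenalidomide and 20.8% with plamotamab, and thrombocytopenia of 31% and 24.0%. Section 4.6.1.1 also allows that lenalidomide may potentiate CRS. If 20 mg in the triplet already produced an unacceptable rate of severe cytopenia, the plan would rely on ad hoc sponsor action to stop the step to 35 and 50 mg.

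**Working it through.** There is no planned figure to reproduce, because this is a rule about sequence. The check sets the calendar, the doses and the existing evidence side by side.

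**Calendar.** The day before C1D1 is Day -1 (Protocol 7.6.1), so there is no Day 0. Elapsed days after a subject's Day -8 dose are (study day + 8 - 1):

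- C1D1: 1 + 7 = 8
- C1D22: 22 + 7 = 29
- C1D28: 28 + 7 = 35
- C2D1 (study day 29): 29 + 7 = 36
- C4D28 (study day 112): 112 + 7 = 119

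Take the last 1A subject's Day -8 as time zero, which is when the 1B trigger is met. That subject first receives plamotamab at day 8. A 1B subject who starts at once reaches 35 mg at day 29 and 50 mg at day 36. By day 29 every 1A subject on schedule has reached C1D22, so most 1A Cycle 1 data exist by then.

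**Doses (Protocol Table 3).**

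| Dose | 1A (mg) | 1B (mg) | Ratio |
|---|---|---|---|
| C1D1 | 0.8 | 0.8 | 1.0 |
| C1D8 | 2 | 2 | 1.0 |
| C1D15 | 20 | 20 | 1.0 |
| C1D22 | 20 | 35 | 1.75 |
| From C2D1 | 20 | 50 | 2.5 |

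Opening 1B early has no dose consequence until C1D22. That is the dose to guard.

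**Existing evidence at these doses (Protocol 2.4.2, 2.4.3).** The monotherapy cohort at 0.8, 2, 20, 35 and 50 mg had 14 subjects. Anemia and lymphopenia were the only Grade 3-4 events seen in more than one subject (2/14 = 14.3%), so Grade 3-4 neutropenia and thrombocytopenia each occurred in at most 1/14. Neither is in the list of events above 20%. Since 3/14 = 21.4% would have been listed, each was at most 2/14 at any grade. For comparison, all 80 NHL subjects had 21.3% neutropenia and 22.5% thrombocytopenia.

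**What a review of 20 subjects in 1A could show.** P(at least 1 event) = 1 - (1 - p)^20, with the matching binomial tail for at least 2. The rates p of a severe event are assumed, and all 20 subjects are taken as evaluable:

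| Assumed p | At least 1 event | At least 2 events |
|---|---|---|
| 5% | 64% | 26% |
| 10% | 88% | 61% |
| 15% | 96% | 82% |
| 20% | 99% | 93% |

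So a problem at 20 mg with a true rate of 10% or more would usually leave some sign in 1A.

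**When to review.** Closing 1B until the last 1A subject reaches C1D28 costs 35 days and gains 35 - 29 = 6 days of data on that subject, compared with a cut at C1D22. If the cut is at day 29 and the review takes r days, the first 1B subject needs only to start r days after the last 1A subject, because that subject's 35 mg dose then falls at day r + 29.

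**The case against.** The strongest reply is that the gap matters little. The 1B schedule starts no higher than 1A, and 50 mg is the recommended monotherapy dose: "No dose-limiting toxicities were observed among the 14 treated subjects", with no Grade 3-4 CRS. Section 2.4 lists CRS at weight-based doses "and at 0.8, 2, 20, 35 mg; however, CRS has not yet been seen at the highest dose levels". The PK predictions in 2.4.3 favor 50 mg over 20 mg on the CRS threshold. That section also explains the two doses as a way to characterize exposure-response, and 2.4.4 names the whole run-in, not the lower dose alone, as the safety assessment. The Medical Monitor or designee must approve each Part 1 subject before treatment (7.4). Table 8 requires all three drugs to be withheld for defined cytopenias. For Grade 3-4 CRS the instruction is "Notify the Xencor Medical Monitor immediately", and serious adverse events are reported within 24 hours.

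Much of this stands, and it lowers the severity. First-dose CRS is not the issue, and the documents give no sign that 50 mg worsens cytopenias. But the 14 subjects received monotherapy. The approval in 7.4 is an eligibility check, and the other safeguards act one subject at a time. None requires a decision about the cohort.

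Three figures invite a stronger reading than they support:

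- The joint evaluation comes at least 119 - 29 = 90 days after the first 35 mg dose if the last 1B subject stays on schedule. That interval is not a measure of benefit from a 1A review, which would not shorten it.
- Zero DLTs in 14 leaves an upper bound of 1 - 0.05^(1/14) = 19% (one-sided 95%, all 14 evaluable). A 1A review holds no data above 20 mg and cannot tighten that bound.
- Cumulative Cycle 1 dose is 57.8 mg in 1B against 42.8 mg in 1A. The difference is 1B exposure, which a 1A review never sees.

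**Conclusion.** The point holds in a moderate form. The plan raises the dose in a combination whose dose it calls unestablished, on an enrollment count alone. No DLT definition, Part 1 stopping rule or criterion for moving from 1A to 1B appears in either document. Section 4.8 does not fill the gap: if Cohort 2 means 1B, the evaluation it relies on already includes 1B, and if it means Part 2, it comes after 1B.

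The exposure concerned is at least 20 subjects, at 1.75 times the 1A dose at C1D22 and 2.5 times from C2D1. This rests on subjects staying on schedule and on 1B starting promptly.

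A reader might infer that nobody would be watching 1A, that 50 mg is an untried dose, or that subjects were exposed to this risk. The documents support none of these. Subject-level oversight is extensive, 50 mg was given as monotherapy, and SAP section 1 reports that the study ended after 3 subjects, against at least 20 needed to complete 1A, so 1B could not have opened under the trigger. This is a cheap improvement to the design as written, at the low end of what should be changed.

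**What to change.** In Protocol 4.1.1 and 4.8, require the sponsor's medical monitor or a named safety group to review cumulative 1A safety data and record a proceed, modify or stop decision before any 1B subject receives the 35 mg dose at C1D22. The data cut should include the last 1A subject through the C1D22 visit or discontinuation. Clinical thresholds are for the sponsor to set.

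Let 1B enroll and receive its first three doses meanwhile. Keep the 0.8, 2, 20, 35, 50 mg step-up, and set 1B start dates so that no subject is held at 20 mg awaiting the decision. In 4.8, replace the undefined Cohort 2 with the cohort or part that is meant.

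The cost is one extra data review and, if 1B would otherwise enroll at once, a stagger equal to the review time: days to a few weeks. A late C1D22 visit in the last 1A subject adds the same delay. No extra subjects, visits or procedures are needed, and the planned dose comparison is unchanged. The review would not catch toxicity that appears only above 20 mg, or later-cycle toxicity in the last 1A subjects. Those still wait for the joint evaluation.
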